6.10. Appendix 10: Rules Applied in Definitions of Endpoints

1. Joint Evaluability Rules for Sign and Symptom Data

For participants having a joint injection(s)/surgical joint procedure(s) prior to the date of study entry (e.g., randomization) or during the study, the affected joint(s) will be valued according to the following rules:

- For participants having a joint injection and/or surgical joint procedure prior to the date of randomization, the affected joints will be analyzed according to the impact of the joint injection and/or surgical joint procedure on the evaluability of the involved joints.
- If a joint is considered un-evaluable at baseline due to certain procedure/injection performed prior to the date of randomization, the joint will be considered un-evaluable throughout the study.
- For participants undergoing joint procedures for the treatment of PsA during the study, the affected joints will be considered as swollen and tender from the date of procedure onwards.
- For participants undergoing joint procedures during the study for the treatment of non-PsA disease indication, the affected joints will be analyzed according to the impact of the surgical joint procedure on the evaluability of the involved joints.
- For participants undergoing joint injections for PsA during the study, the affected joints will be considered as swollen and tender from the date of injection for the next 90 days.
- For participants undergoing joint injections for non-PsA related reasons during the study, the affected joints will be considered as non-evaluable from the date of injection for the next 90 days.

2. Joint Count Adjustment Rule

For participants who have an incomplete set of evaluable joints the joint count/score will be adjusted to the total number joints of interest (e.g., 68 joints for tenderness and 66 joints for swelling) by dividing the number of affected joints by the number of evaluable joints and multiplying by the total number joints of interest.

3. LLOQ rule

Any value < LLOQ is considered equal to half of the value of LLOQ for numerical calculations.

4. Joint Evaluability Rules for Radiographic Data

A joint may be not evaluable due to surgery/joint replacement or radiographically insufficient data for reading. Joints with surgery/joint replacement or with radiographically insufficient data for reading will be considered as not evaluable for joint erosion/JSN.

For a joint that is considered as not evaluable at a given time point, both the joint-level erosion score and the joint-level JSN score will be set to missing at the said time point.

5. Erosion and JSN Score Adjustment Rules

The regional erosion and JSN scores for hands and feet will be determined based on the evaluable joints. For participants who have an incomplete set of evaluable joints at a given time point, each reader's regional erosion and JSN scores at the said time point will be adjusted using the following rules:

Rules for Adjustment of Erosion Scores by Region	
Region	Adjustment for the incomplete set of evaluable joints
Hands/Wrists (40 joints)	
 • If total number of joints evaluable at the given time point is ≥ 20 (i.e., 50% of 40), then the erosion score for hands/wrists will be obtained by calculating the average erosion score for hands and wrists and multiplying with 40. • If the total number of joints evaluable at the given time point is < 20, then the erosion score for hands and wrists will be set to missing.
Feet (12 joints)	
 • If total number of joints evaluable at the given time point is ≥ 6 (i.e., 50% of 12), then the erosion score for feet will be obtained by calculating the average erosion score for feet and multiplying with 12. • If the total number of joints evaluable at the given time point is < 6, then the erosion score for feet will be set to missing.

Rules for Adjustment of JSN Scores by Region	
Region	Adjustment for the incomplete set of evaluable joints
Hands/Wrists (40 joints)	
 • If total number of joints evaluable at the given time point is ≥ 20 (i.e., 50% of 40), then the JSN score for hands/wrists will be obtained by calculating the average JSN score for hands and wrists and multiplying with 40. • If the total number of joints evaluable at the given time point is < 20, then the JSN score for hands and wrists will be set to missing.
Feet (12 joints)	
 • If total number of joints evaluable at the given time point is ≥ 6 (i.e., 50% of 12), then the JSN score for feet will be obtained by calculating the average JSN score for feet and multiplying with 12. • If the total number of joints evaluable at the given time point is < 6, then the JSN score for feet will be set to missing.

A reader's modified vdH-S score is the sum of the reader's erosion and JSN scores of both hands and feet. If a reader's regional score is missing for any region of erosion or JSN, the reader's modified vdH-S score will be set to missing.

6. Reader Confirmation Rules

For each participant, let $\Delta 1$ and $\Delta 2$ stand for the change from baseline in modified vdH-S score, respectively, of primary readers 1 and 2 at any post-baseline visit (i.e., Week 24 in Read Campaign 1, Weeks 24 or 48 in Read Campaign 2, and Week 24, 48, or 96 in Read Campaign 3, and Week 24, 48, 96, or 156 in Read Campaign 4). If the absolute difference between $\Delta 1$ and $\Delta 2$ is greater than or equal to 3 (i.e., $|\Delta 2 - \Delta 1| \geq 3$), or either $\Delta 1$ or $\Delta 2$ is missing (but not both $\Delta 1$ and $\Delta 2$ are missing), a confirmation reader (a third reader) will then read all the radiographic images (including baseline and post-baseline images) in that given read campaign from that participant.

7. Reader Selection Rules

For participants who require confirmation (i.e., there are readings from 3 readers), the scores from 2 selected readers will be used in the analysis.

Let $\Delta 1$, $\Delta 2$, and $\Delta 3$ stand for the change from baseline in modified vdH-S score at Week 24, respectively, of primary reader 1 (Reader 1), primary reader 2 (Reader 2), and the confirmation reader (Reader 3). The 2 readers whose scores will be used in the analysis will be selected from the 3 readers based on the criteria specified in the table below.

Rules for Selection of Readers Following Confirmation	
Scenarios based on change from baseline in modified vdH-S score at Week 24	Readers whose scores will be used for the analysis at each visit
$ \Delta 3 - \Delta 1 < \Delta 3 - \Delta 2 $	Reader 1 and confirmation reader (Reader 3)
$ \Delta 3 - \Delta 2 < \Delta 3 - \Delta 1 $	Reader 2 and confirmation reader (Reader 3)
$ \Delta 3 - \Delta 1 = \Delta 3 - \Delta 2 $	Reader 1 and Reader 2
$\Delta 1$ is missing but $\Delta 2$ and $\Delta 3$ are non-missing	Reader 2 and confirmation reader (Reader 3)
$\Delta 2$ is missing but $\Delta 1$ and $\Delta 3$ are non-missing	Reader 1 and confirmation reader (Reader 3)
$\Delta 3$ is missing but $\Delta 1$ and $\Delta 2$ are non-missing	Reader 1 and Reader 2
Both $\Delta 1$ and $\Delta 3$ are missing, but $\Delta 2$ is non-missing	Reader 1 and confirmation reader (Reader 3)
Both $\Delta 2$ and $\Delta 3$ are missing, but $\Delta 1$ is non-missing	Reader 2 and confirmation reader (Reader 3)

8. Smallest Detectable Change

Smallest Detectable Change (SDC) is the smallest change in a score that is considered to be assessed correctly based on the limits of agreement (ie, above the measurement error) (Bruynesteyn 2005).

The SDC in score of interest is determined as follows:

$$SDC = 1.96 * SD / (\sqrt{2} * \sqrt{k}), \text{ where}$$

- SD is the standard deviation of the difference between the 2 selected readers in change from baseline in the score of interest
- $k = 2$, is the number of readers

6.11. Appendix 11: Summary of Analyses Based on Multiple Imputation

Table 17: Summary of Multiple Imputation Method

Endpoints (Population ^a) Estimand ^b	MI specification	Analysis method/Summary statistics
ACR20 at Week 24 (mFAS) Adjusted Composite Estimand	Multiple imputation with FCS regression of component scores	MIdat_ACR1 (N=200, Seed ^d =18496) • Imputation variables: 7 ACR components from Week 0 - Final scheduled visit of the DBL. • Ancillary variables: Intervention group, randomization strata levels
ACR20 at Week 24 (FAS) Adjusted Composite Estimand	Multiple imputation with FCS regression of component scores	MIdat_ACR2 (N=200, Seed ^d =877681) • Imputation variables: 7 ACR components from Week 0 - Final scheduled visit of the DBL. Ancillary variables: Intervention group, randomization strata levels
ACR20 at Week 24 (mFAS-UKR) Treatment Policy Estimand	Multiple imputation with FCS regression of component scores	MIdat_ACR3 (N=200, Seed ^d =39982) • Imputation variables: 7 ACR components from Week 0 - Final scheduled visit of the DBL. Ancillary variables: Intervention group, randomization strata levels
Modified vdh-S, erosion, JSON (mFAS) Adjusted Treatment Policy Estimand	Multiple imputation with FCS regression of component scores	MIXdat_VDH1 (N=200, Seed ^d =25940) • Imputation variables: hand erosion, foot erosion, hand JSON, and foot JSON from baseline – Final scheduled visit of the DBL. • Ancillary variables ^c : intervention group, randomization stratification factors, and 7 ACR component overtime through Week 24
Modified vdh-S, erosion, JSON (FAS) Adjusted Treatment Policy Estimand	Multiple imputation with FCS regression of component scores	MIXdat_VDH2 (N=200, Seed ^d =12783) • Imputation variables: hand erosion, foot erosion, hand JSON, and foot JSON from baseline – Final scheduled visit of the DBL. • Ancillary variables ^c : intervention group, randomization stratification factors, and 7 ACR component overtime through Week 24
Modified vdh-S, erosion, JSON (mFAS-UKR) Treatment Policy Estimand	Multiple imputation with FCS regression of component scores	MIXdat_VDH3 (N=200, Seed ^d =928374) • Imputation variables: hand erosion, foot erosion, hand JSON, and foot JSON from baseline – Final scheduled visit of the DBL. Ancillary variables ^c : intervention group, randomization stratification factors, and 7 ACR component overtime through Week 24

^a The population defines which subset of participants the imputation will be performed for.

^b The handling of ICEs associated with the estimand listed will be applied to the imputation variables and ancillary variables (if post-baseline) prior to imputation.

^c For the modified vdh-S score which is assessed infrequently compared to other assessments, the 7 ACR components are included in the list of the ancillary variables since they may be related to the mechanism leading to missing data.

^d The starting seed for FCS regression MI is used to generate a series of imputation seeds using the algorithm: $\text{INT}((2^{**31-2})*\text{RANUNI}(\text{starting seed}))$, where each imputation seed will be used for a single imputation. To account for the possibility that some imputations may fail to complete due to out-of-range issues, 200+ initial imputation seeds will be prepared, and the first 200 successful imputations will be used for analysis.

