For change from baseline in modified vdH-S score, participants in each treatment group can be considered a mixture of two subpopulations: one subpopulation (Spop 1) with a change score of 0 regardless of treatment and another subpopulation (Spop2) with a change score sampled from a normal distribution. Therefore, the distribution of the modified vdH-S change scores is determined by 3 parameters: the probability that a participant has a change score of 0, the mean of the normal distribution, and the standard deviation (SD) of the normal distribution. The overall mean (ie, crude mean) of the change scores for a treatment group is the overall average of the change scores among all participants (including both Spops 1 and 2) in that treatment group.

In the PSA3002 study, the following statistics were observed for change from baseline in modified vdH-S score at Week 24 for each treatment group:

The overall mean (SD) of change from baseline in modified vdH-S score at Week 24 was 0.90 (3.14), 0.25 (2.52), and 0.45 (2.38) respectively, for the placebo, guselkumab 100 mg q4w, and guselkumab 100 mg q8w treatment groups. The assumptions for power calculations in this study are based in part on these data, adjusted for the difference in enrichment criteria between studies.

For this study, assuming an overall mean (SD) of change from baseline in modified vdH-S score as 1.13 (3.2), 0.25 (3.1), and 0.45 (3.1) respectively in the placebo, guselkumab 100 mg q4w, and guselkumab 100 mg q8w groups, a sample size of 350/250/350 participants (ie, 7:5:7 ratio, 950 in total) will provide a power of at least 90% and 80% to detect a significant treatment difference at a 2-sided significance level of $\alpha=0.05$ for guselkumab q4w vs placebo and guselkumab q8w vs placebo comparisons respectively.

Table 4 provides the statistical power for guselkumab 100mg q4w vs placebo under various assumptions, where the sample size is 250 in the guselkumab group and 350 in the placebo group.

Table 4: Statistical Power for Treatment Difference in Modified vdH-S Change from Baseline at Week24 for Guselkumab 100mg q4w vs Placebo (N=250, 350)

Percent Participant with extra 0 (Spop 1)	Normal Placebo (Spop 2)		Normal Guselkumab (Spop 2)		Overall Placebo		Overall Guselkumab		Overall Mean Difference	Power
	Mean	SD	Mean	SD	Mean	SD	Mean	SD		
15%	1.33	3.4	0.29	3.4	1.13	3.2	0.25	3.1	-0.88	92
15%	1.33	3.4	0.34	3.4	1.13	3.2	0.29	3.1	-0.84	89
15%	1.33	3.0	0.29	3.0	1.13	2.8	0.25	2.8	-0.88	96

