5.3.3.2. Multiplicity Adjustment for Testing Procedures

This study has 1 primary endpoint (proportion of participants who achieved an ACR 20 response at Week 24) and 1 key confirmatory secondary endpoint (change from baseline in modified vdH-S score at Week 24). With 2 treatment comparisons each, there are a total of 4 hypotheses to be tested. These hypotheses are explicitly listed in Section 2.

The overall Type I error of these 4 hypotheses will be controlled at a significance level of ≤ 0.05 . The testing procedure tests the primary and key confirmatory secondary endpoints, for the two regimens of guselkumab vs placebo, in a fixed sequence and each endpoint is tested at the two sided 0.05 level of significance. The fixed sequence testing method tests an endpoint only if the null hypotheses of no difference between the guselkumab regimen and placebo was rejected at the 0.05 level for all the endpoints above it in the sequence. This is shown visually in Figure 2 below.

Figure 2: Multiplicity Control

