For participants experiencing multiple ICEs, an ICE in categories 4 or 5 (ie, using the hypothetical strategy) will supersede an ICE in categories 1, 2, 3, and 6 (ie, using the treatment policy strategy) will supersede an ICE in categories.

These ICE strategies are also summarized in tabular form in Section 6.14.

Handling Rules for Missing Continuous Data for Adjusted Treatment Policy Estimand

1. **Missing data for any reason** will be assumed to be MAR. The FCS MI method is used to impute the missing component data, and the total score is derived from the sum of components.

Handling Rules for Missing Binary Response Data for Adjusted Treatment Policy Estimand

1. **Missing data for any reason** will be assumed to be MAR. The FCS MI method is used to impute the missing component data, and the total score is derived from the sum of components. The result is dichotomized into the binary response.

Analysis Testing for Adjusted Treatment Policy Estimand

Statistical comparison between a guselkumab group (100 mg q4w or 100 mg at Weeks 0, 4 and then q8w) and the placebo group will be performed at Week 24 using Read Campaign 1 data. No treatment comparison will be performed after Week 24, or using the other read campaign data; only descriptive summaries by study intervention and visit will be presented.

Table 14 summarizes the analyses for supportive efficacy endpoints related to joint structural damage, the methods for analyses, and the data handling rules used.

Table 14: Summary of Estimands, Analysis Sets, Data Handling Rules, and Analysis Methods for Endpoints of Joint Structural Damage

	Endpoint	Analysis Set	Missing Data Rules	Analysis Methods
ENDPOINTS AT WEEK-24 DBL USING READ CAMPAIGN 1, ADJUSTED TREATMENT POLICY ESTIMAND				
1	Change from baseline in modified vdH-S erosion score, JSN score at Week 24	mFAS	FCS MI for MAR	
 Summarized descriptively Combined ANCOVA results across imputation sets, including: LS mean (95% CI) for each intervention group, LS mean difference (95% CI) and p-values for differences between groups
2	Proportion of participants with change ≤ 0 from baseline in modified vdH-S score at Week 24	mFAS	FCS MI for MAR	
 Summarized descriptively Combined CMH statistic^a across imputation sets for p-value Response rates, and treatment difference in response rates and 95% CI, based on combined results across imputation sets.

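### The vdH-S imputation does not state its range limits and cannot reproduce zero change, so the change ≤0 and ≤0.5 proportions are understated and, if draws are floored at 0, arm means are inflated

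*SAP*

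**What the plan says.** SAP Section 6.11 (Appendix 11), Table 17, gives the method for hand and foot erosion and hand and foot JSN as "Multiple imputation with FCS regression of component scores", with 200 imputations. Footnote d, attached to the seeds of every row (three ACR, three vdH-S), reads in part: "some imputations may fail to complete due to out-of-range issues, 200+ initial imputation seeds will be prepared, and the first 200 successful imputations" (these are the ones analysed). No minimum, maximum, redraw, rounding or failure-rate rule is given.

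These draws feed two uses. Section 5.3.5.1.3 analyses change in the total score by ANCOVA on each imputed dataset, for H3 and H4. Section 5.3.6.6.2 sums the imputed components for the binary radiographic endpoints, and then "The result is dichotomized into the binary response". Table 14 applies this to change ≤0, change ≤0.5 and no progression beyond the SDC, at Week 24 and through Week 156.

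The plan itself expects a spike at zero. The power model in Section 3.1.2 includes "one subpopulation (Spop 1) with a change score of 0 regardless of treatment", set at 15% or 25%. Protocol Section 4.3 reports that about two thirds of PSA3002 participants did not progress.

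**The concern.** An unrestricted normal regression has no range to leave, so a failure for being out of range makes sense only if limits are imposed. Low sub-scores are plausible in this population: inclusion criterion 5 asks for only two eroded joints, with no requirement on JSN or the feet, and the NP stratum takes participants with five or fewer eroded joints. For a participant at or near 0, a floor at 0 lets the draw move only upward, so someone who would have been unchanged is imputed as a progressor.

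A second problem does not depend on any limit. A continuous draw has practically no chance of giving exactly zero change. When such draws are cut at ≤0 or ≤0.5, participants who belong to the spike are spread across the cut, and many fall on the progressing side.

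The imputed group is wider than the dropouts. Films outside ±2 weeks of Week 24 are not used in the main analysis, and data after ICEs 4 and 5 are set aside and imputed.

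**Working it through.** **1. The plan's own figure.** Inputs from SAP Section 3.1.2: overall mean (SD) change 1.13 (3.2) placebo, 0.25 (3.1) q4w, 0.45 (3.1) q8w; 350/250/350; two-sided 0.05. Power ≈ Φ(|difference|/SE − 1.96).

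- q4w: SE = √(3.2²/350 + 3.1²/250) = 0.260; Φ(0.88/0.260 − 1.96) ≈ 92%.
- q8w: SE = √(3.2²/350 + 3.1²/350) = 0.238; Φ(0.68/0.238 − 1.96) ≈ 81%.

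Ten thousand simulations of the zero/normal mixture with the van der Waerden test give 92.1% and 80.9%, against the stated 92 and 80. The mixture is therefore understood as the plan uses it.

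**2. Loss of the zero spike, with no limit and no assumed baselines.** Under the plan's mixture, P(change ≤ c) = 0.15 + 0.85 Φ((c − μ)/3.4), with μ = 1.33, 0.53 and 0.29 for placebo, q8w and q4w. A single normal with the same overall mean and SD gives Φ((c − mean)/SD).

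| | ≤0, mixture | ≤0, normal | ≤0.5, mixture | ≤0.5, normal |
|---|---|---|---|---|
| Placebo | 0.45 | 0.36 | 0.49 | 0.42 |
| q8w | 0.52 | 0.44 | 0.57 | 0.51 |
| q4w | 0.55 | 0.47 | 0.60 | 0.53 |

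**3. Simulation of sub-score imputation.** The documents give neither the sub-score distributions nor the missing rates, so these are assumed: skewed or zero-inflated baselines (component means 10/5/8/2 or 20/8/14/4 in some runs; 15 to 45% zeros in others), 5 to 10% missing, scores in 0.5 steps where rounding was applied. Each run compares draws floored at 0 with unlimited draws. Strata and ACR ancillary variables were left out of at least one of the runs.

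- *Mean change of imputed participants.* Floored: too high by 0.51 to 1.07 in one set of runs, 0.83 in another, about 1.2 in a third. Unlimited: about 0.
- *Arm mean, floored.* Too high by 0.03 to 0.05 at 5% missing and 0.06 to 0.10 at 10%. Unlimited: −0.01 to +0.01.
- *Treatment difference, equal missingness.* Floored: 0.00 to +0.015.
- *Treatment difference, unequal missingness.* If b is the upward error per imputed participant, the difference (guselkumab minus placebo) moves by (p_gus − p_pbo) × b. At 5% versus 10% this is −0.05b, or −0.025 to −0.06 for b from 0.5 to 1.2. Simulated: −0.03 to −0.06, also with no true effect; rates reversed, +0.02 to +0.07; unlimited, within 0.005 of zero.
- *Share of imputed participants with change ≤0.* With the plan's 15% mixture: 0.19 to 0.29 floored and 0.32 to 0.39 unlimited, against 0.49 to 0.55 true. With about 63% exact zeros the shortfall is larger: 0.21 to 0.34 floored and 0.33 to 0.45 unlimited, against 0.70 to 0.81.
- *Share with change ≤0 in the whole arm.* Shift = missing fraction × (imputed share − true share). Example: 10% × (0.21 − 0.51) = −3.0 points floored; 10% × (0.35 − 0.51) = −1.6 points unlimited. Across the runs with 5 and 10% missing: 1.2 to 5.1 points lower floored, 0.7 to 3.9 unlimited.

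**4. The discard rule.** With up to 100 redraws allowed, no imputation failed; the most redraws needed was 49. At an even chance of being in range, 100 straight misses have probability 0.5^100 ≈ 8 × 10⁻³¹.

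**5. Which variable to match on.** Predictive mean matching on the Week 24 level restored only about half of the exact zeros and biased the mean by about −0.5 to −0.7. The matching should therefore be on change from baseline.

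**The case against.** The limits are an inference. Footnote d serves the ACR rows as well and is worded as a contingency. If no limit is applied to vdH-S, the mean is not biased. This stands, and it makes the inflation of the mean conditional.

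A reader might infer that keeping the first 200 successes selects imputations and so biases the result. The documents do not support that: they give no failure rate, and the check found no failure.

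A reader might also infer that H3 and H4 are materially biased. They test differences, which barely move unless missingness differs by arm, and the documents give no such rates. The protocol asks for Week 24 films even after treatment stops, and ICEs 1 to 3 use observed data. A shift of 0.04 is 0.04/0.238, about 0.17 standard errors for q8w, although SAP Table 5 does show power falling from 80 to 75 when the difference shrinks from −0.68 to −0.64. The tipping-point analyses vary the two arms independently and would probe such a shift. The first of them, however, holds ICE 4/5 imputations fixed, and neither addresses the responder endpoints. Sensitivity Analysis 8 changes the imputation for the total score only.

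Two further points are fair. Criterion 5 and two-reader averaging make very high zero rates in sub-scores doubtful. The no-progression endpoints carry nominal p-values (Section 5.3.6), and a spike at zero does not sit at the SDC cut, so no understatement is shown there.

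**Conclusion.** The firm part is the responder endpoints. Continuous normal draws cannot reproduce zero change, so the change ≤0 and ≤0.5 proportions are understated among imputed participants whether or not limits apply. For ≤0, the imputed share is about 0.2 with a floor and 0.35 to 0.4 without, against about 0.5 true under the plan's 15% mixture. Per arm this is roughly 1 to 5 points at 5 to 10% missing. Table 14 schedules no alternative imputation for these endpoints.

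The conditional part is the mean. If the vdH-S draws are floored at 0, imputed change is too high by roughly 0.5 to 1.2 points each. That inflates arm means, and shifts the confirmatory difference by only about 0.03 to 0.07 at 10% versus 5% missing, in the direction set by which arm misses more films.

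The sizes rest on assumed baseline sub-scores and missing rates. The documents do not support reading this as an established bias in H3 or H4, or as a selection effect of the discard rule. The gap in specification is real: the imputation behind two hypotheses for which "each endpoint is tested at the two sided 0.05 level of significance" does not state its bounds.

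**What to change.** For the ANCOVA endpoints, state in Table 17 that the vdH-S FCS regression uses no minimum or maximum and that all 200 pre-specified imputations are analysed. Out-of-range draws do no harm to a mean, and without limits there is nothing to fail for being out of range.

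For the ≤0, ≤0.5 and SDC responder endpoints, impute the sub-score changes from baseline, not the Week 24 levels, by FCS predictive mean matching, so that the spike at zero change is largely kept.

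The cost is SAP wording, a second imputed dataset with its own seed and specification, and some imputed sub-scores slightly outside the scoring range in the ANCOVA dataset. The two datasets will not agree participant by participant, and the SAP should say so.
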